10. DATA PRESENTATION

The report forms part of an integrated clinical study report. The actual numbering of tables, listings and other outputs may change. Numbering is in accordance with ICH guideline E3².

10.1 Procedure or treatment labels

The following labels will be used for all output: **EVARREST** and **SURGICEL**.

10.2 Tables and figures

Data will be tabulated by treatment group and, if appropriate, by visit. Continuous data summaries will present (unless stated otherwise) number of observations, number of missing observations (if there are any), mean, standard deviation, minimum, median and maximum. Categorical data summaries will present the number of observations and the corresponding percentage. The following tables will be produced:

10.2.1 In-text tables and figures

These will be produced for the main report in conjunction with the medical writer. These will include, but will not be limited to:

| No | Title of table/figure | Notes |
|----|--|--|
| F1 | Subject disposition | Based on Table 14.1.1.4 |
| T1 | Demographic characteristics – FAS analysis set | Summary of Table 14.1.2.1 |
| T2 | Surgical procedure – FAS analysis set | Summary of key items from Tables 14.1.3.1-14.1.3.7 |
| T3 | Statistical summary for primary effectiveness endpoint – Per-Protocol and FAS analysis sets (including sensitivity analysis summary) | Summary of Tables 14.2.1.1 and 14.2.1.2 |
| T4 | Summary of AEs occurring in >5% of subjects – Safety analysis set | Summary of 14.3.1.3 |

T=Table F=Figure

10.2.2 Section 14 tables

Shell tables shown in Appendix 1, according to the code in the 'Shell' column. All table numbers will be prefixed with 14.

| No | Title of table/figure | Notes | Shell ¹ |
|-------|--|---------------------------------------|--------------------|
| 1.1 | Disposition of subjects, analysis sets and protocol deviations | | |
| 1.1.1 | Disposition of subjects by centre – FAS | Includes number withdrawn – by center | DS |

¹ Shell: Example table from Appendix 1 (Shell tables). Letters refer to standard output, numbers to project specific output.

| No | Title of table/figure | Notes | Shell ¹ |
|-------|--|---|--------------------|
| 1.1.2 | Enrollment by center – FAS | By center | E |
| 1.1.3 | Summary of protocol deviations – FAS | Includes both minor and major protocol deviations | PD |
| 1.1.4 | Analysis sets – FAS | | ST |
| 1.2 | Baseline data | Excludes baseline data that is also measured post procedure and/or safety data | |
| 1.2.1 | Demographics – FAS | Age, height, weight, BMI – continuous data (c); gender, race, ethnicity, and indication of subject being of child bearing age – all discrete data (d) | DG |
| 1.2.2 | Baseline characteristics – FAS | Presence of relevant history of prior surgery, indication of any relevant changes in medical history between screening and 24 hours before procedure, and confirmation of subject eligibility - all (d) | G1 ² |
| 1.2.3 | Physical exam / medical / surgical history – FAS | Includes frequencies | HX |
| 1.3 | Operative data | | |
| 1.3.1 | Operative data: Surgery details, transfusions, and randomization – FAS | Primary operative procedure, treatment to which subject is randomized (both d), estimated intraoperative blood loss (mL) (c), indication of subject receiving blood or blood product transfusions from surgery through hospital discharge (d), indication of cell saver usage (d), and cell saver volume (mL) collected and returned (c) | G2 |
| 1.3.2 | Operative data: Target Bleeding Site (TBS) identification – FAS | Primary method to obtain hemostasis at the TBS (d), TBS length (cm), width (cm), area (cm ²) (all c), and location (d), type of bleeding (d), TBS tissue type (d); for liver only TBS: estimated total transected plane area (cm ²) (c), estimated portion of total transected plan area which is treated, reason for liver resection, type and location of resection at TBS, hepatic parenchyma classification/type and specification (if abnormal), predominant source of bleeding, type of arterial bleeding, type of venous bleeding, area of bleeding and specification (if “diffuse”) (all d) | G2 |
| 1.3.3 | Operative data: Treatment application – FAS | Approximate length and width of product applied at the TBS (cm), TBS area (cm ²), and size of EVARREST implanted (cm ² per kilogram of body weight) (all c); For patients treated with EVARREST: total number of EVARREST units used at TBS (both c and d), indication of appropriate identification of TBS, presence of adequate access to TBS, indication of sufficient coverage of TBS, indication of EVARREST pads overlap at TBS, including number of overlap locations and presence of sufficient overlap, surgeon’s ability to properly apply EVARREST at its first application to TBS, and reasons for incorrect EVARREST application (all d); For patients treated with SURGICEL: number of kits used at TBS (both c and d) and indication of SURGICEL use according to IFU (d) | G2 |

² For Tables G1, G2, G3 notes will indicate if data is continuous or discrete.

| No | Title of table/figure | Notes | Shell ¹ |
|-------|--|--|--------------------|
| 1.3.4 | Operative data: Hemostasis assessments – FAS | Time from randomization to initial application of hemostatic product with manual compression (sec) (c), TBS hemostasis presence at 4 and 10 minutes from randomization (both d), absolute time to hemostasis (from randomization) (sec) (c), and presence of any bleeding at TBS between 4 minutes from randomization and final fascial closure (d) | G2 |
| 1.3.5 | Operative data: Bleeding/durability details – FAS | For patients with bleeding at TBS between 4 minutes following randomization and final fascial closure: type of bleeding, indication of additional treatment required to assure durability of hemostasis, and indication of any re-treatment due to application error (all d) | G2 |
| 1.3.6 | Operative data: Additional treatments – FAS | Reason for any additional treatment used at the TBS (d), time from randomization to re-bleed (c), and treatments applied (d); for patients re-treated with EVARREST, approximate length and width of EVARREST used (cm) (both c) | G2 |
| 1.3.7 | Operative data timings and other durations – FAS | Time in operating room (min), length of procedure (from first incision to last suture/staple) (min), length of procedure measured as time from first incision to initiation of fascial closure (when applicable) (min), time from screening visit to hospital admission (days), time from baseline visit to hospital admission (days), time from screening visit to surgery (days), time from baseline visit to surgery, and time from surgery to 30-day visit (days) (all c); For liver resections patients: time from start of liver resection to last suture/staple (min) and time from start of liver resection to initiation of final fascial closure (when applicable) (min) (both c) | G2 |
| 2 | Effectiveness data | | |
| 2.1 | Primary endpoint: Absolute time to hemostasis, elapsed from randomization | Includes analysis by treatment group and pediatric group, as well as by treatment group and age group; Includes analysis separately for subjects who achieved hemostasis with and without additional randomized treatments being required; Includes 95% CIs for median absolute time to hemostasis, reported separately for EVARREST and Control groups | |
| 2.1.1 | Primary effectiveness analysis: Absolute time to hemostasis, elapsed from randomization – FAS | Continuous data | G2 |
| 2.1.2 | Primary effectiveness analysis: Absolute time to hemostasis, elapsed from randomization – PP set (supportive analysis) | Continuous data | G2 |
| 2.2 | Secondary effectiveness endpoints | | |

| No | Title of table/figure | Notes | Shell ¹ |
|-------|---|---|--------------------|
| 2.2.1 | Hemostasis at 4 minutes following randomization and no bleeding requiring treatment at the TBS occurs any time prior to final fascial closure – FAS | Discrete data Includes 95% CI for proportion of subjects with hemostasis at 4 minutes separately for each group, as well as 95% CI for the ratio of proportions | G2 |
| 2.2.2 | Hemostasis at 10 minutes following randomization and no bleeding requiring treatment at the TBS occurs any time prior to final fascial closure – FAS | Discrete data Includes 95% CI for proportion of subjects with hemostasis at 10 minutes separately for each group, as well as 95% CI for the ratio of proportions | G2 |
| 2.2.3 | Proportion of subjects with no re-bleeding at the TBS – FAS | Discrete data | G2 |
| 2.3 | Follow-up assessments | | |
| 2.4 | Post-surgery to hospital discharge (within 72 hours prior to discharge) and 30-day (\pm 14 days) follow-up assessments – FAS | Indication of re-hospitalizations since hospital discharge, indication of surgical procedures since hospital discharge, indication of transfusions since hospital discharge [all for 30-day (\pm 14 days) visit only] (all d), indication of relevant changes in medical history since screening (d), presence of clinically significant changes to subject since baseline (d), subject presence in elevated care unit (ICU, step-down unit, etc.) (d), duration of subject presence in elevated care unit (ICU, step-down unit, etc.) (c), subject presence on ventilator post-operatively (d), duration of subject being on ventilator post-operatively (c), length of subject hospital stay from admission to discharge (days) (c), and length of subject hospital stay from procedure to hospital discharge (days) (c) | G2 |
| 3 | Safety data | | |
| 3.1 | Adverse Events | | |
| 3.1.1 | Number of subjects experiencing any during/post treatment AE by category – Safety analysis set | | AS |
| 3.1.2 | Adverse events (during/post treatment) by subject, MedDRA preferred term and system organ class – Safety analysis set | | AM |
| 3.1.3 | Summary of during/post treatment adverse events by subject and coded terms, preferred terms occurring in $\geq 5\%$ of subjects – Safety analysis set | | AM |

| No | Title of table/figure | Notes | Shell ¹ |
|-------|--|---|--------------------|
| 3.1.4 | Summary of during/post treatment serious adverse events by subject and coded terms – Safety analysis set | Includes adverse events for which the answer for CRF question “Serious?” in the CRF is “Yes” | AM |
| 3.1.5 | Summary of during/post treatment surgical procedure related (possibly, definitely) adverse events by subject and coded terms – Safety analysis set | Includes adverse events for which the answer for CRF item “Relationship to surgical procedure” is “Possibly related” or “Related”. | AM |
| 3.1.6 | Summary of during/post treatment study treatment related (possibly, definitely) adverse events by patient and coded terms – Safety analysis set | Includes adverse events for which the answer for CRF item “Relationship to study treatment” is “Possibly related” or “Related”. | AM |
| 3.2 | Laboratory data | Reported in SI units | |
| 3.2.1 | Laboratory data: Full Blood Count - Safety analysis set | At screening, at baseline, and post-surgery to hospital discharge - within 72 hours prior to discharge) | L |
| 3.2.2 | Laboratory data: White Blood Cell Differential - Safety analysis set | At screening, at baseline, and post-surgery to hospital discharge - within 72 hours prior to discharge) | L |
| 3.2.3 | Laboratory data: Coagulation Parameters - Safety analysis set | At screening, at baseline, and post-surgery to hospital discharge - within 72 hours prior to discharge) | L |
| 3.3 | Other safety data | | |
| 3.3 | Safety/secondary endpoints – Safety analysis set | Proportion of subjects with adverse events that are potentially related to bleeding at the TBS, proportion of subjects with adverse events that are potentially related to thrombotic events, proportion of subjects with re-treatment at the TBS (all d), estimated intra-operative blood loss (mL) (c), and volume of blood and blood products transfusions (red blood cells, whole blood, fresh frozen plasma, platelets, and cryoprecipitates), intra-operatively, prior to hospital discharge, and after discharge (all c) | G2 |

Note: ‘–’ indicates a new line in the title.

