4.2 Inclusion Criteria

Pre-operative:

1. Paediatric subjects aged ≥ 28 days (≥ 1 month) to <18 years, requiring non-emergent open hepatic, abdominal, retroperitoneal, pelvic or thoracic (non-cardiac) surgical procedures;
 - i) The first 36 subjects to be enrolled will be subjects aged ≥ 1 years to <18 years.
 - ii) The next 4 subjects to be enrolled will be subjects aged ≥ 28 days to <1 year.
2. The subject's parent/legal guardian must be willing to give permission for the subject to participate in the trial, and provide written Informed Consent for the subject. In addition, assent must be obtained from paediatric subjects who possess the intellectual and emotional ability to comprehend the concepts involved in the trial. If the paediatric subject is not able to provide assent (due to age, maturity and/or inability to intellectually and/or emotionally comprehend the trial), the parent/legal guardian's written Informed Consent for the subject will be acceptable for the subject to be included in the study.

Intra-operative

3. Presence of an appropriate mild or moderate bleeding soft tissue or hepatic parenchyma Target Bleeding Site (TBS) identified intra-operatively by the surgeon;
4. Ability to firmly press trial treatment at TBS until 4 minutes after randomisation;

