5.2 Procedures

ETHICON will provide each site with computer-generated randomisation envelopes, each bearing the subject randomisation number, and containing the treatment allocation.

Treatment will be assigned randomly to each subject on a 1:1 basis to either EVARREST or SURGICEL treatment.

In the event that a potential subject fails intra-operative criteria (i.e. no TBS identified, or an intra-operative exclusion), and is not randomised to the study, the unused randomisation envelope should be returned to the series, and used for the next subject.

Given the difference between the EVARREST and SURGICEL treatment groups, it will not be possible for the surgeon to be blinded to the treatment. However, to avoid any bias in the conduct of the surgical procedure, randomisation should only take place after completion of the following steps:

1. EVARREST and SURGICEL will be prepared and available in the sterile field in the operating room, ready for administration for each patient.
2. The investigator must perform the surgical procedure according to his/her standard of care.

⁵ Appendix 1

3. Once the investigator encounters an appropriate hepatic parenchyma or soft tissue TBS related to the primary operative procedure, randomisation should immediately take place. The randomisation envelope will be opened simultaneously with starting the stopwatch.

If the subject is randomised to SURGICEL then the unused EVARREST treatment product MUST immediately be removed from the sterile field and placed for destruction. After the procedure accountability of the product should be documented.

If additional soft tissue bleeding sites requiring a topical haemostatic product are identified after the treatment of the initial target bleeding site, these bleeding sites should be treated according to the surgeon's standard of care.

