7.2 Procedures for Handling Biological Samples

7.2.1 Laboratory Tests

All laboratory investigations for FBC and Coagulation parameters will be performed at the local hospital laboratory. The volume of blood to be taken will be determined according to the standard practices of each hospital. The normal reference ranges and laboratory accreditation certificates must be provided to ETHICON. Local labs will be performing the tests in a blinded fashion as the local labs will not be aware of the randomised treatment.

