8.4.2 Methods of Analysis

Adverse events will be summarized descriptively by the treatment received, using Medical Dictionary for Regulatory Activities (MedDRA) terminology.

Laboratory values (including coagulation parameters) will be reported in International System (SI) units. Values and changes from baseline will be listed and summarized. Clinically significant changes will be reported as part of the AE summary.

AEs (MedDRA terminology) will also be summarized into Infants and toddlers (28 days to 23 months), Children (2 to 11 years) and Adolescent (12 to <18 years).

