8.2.1 Sample size justification

No formal sample size calculation has been performed for this study. The sample size required for the trial is at least 40 randomized paediatrics subjects recruited from sites within the European Union and Canada. This sample size is considered adequate to achieve the study objectives and provide sufficient information to evaluate data descriptively.

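### As specified in the SAP text, the laboratory tables pool raw SI values across ages and local laboratories, with no count of out-of-range results by arm and no summary of change from baseline

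*SAP*

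**What the plan says.** Protocol section 7.2.1 describes no central laboratory: "All laboratory investigations for FBC and Coagulation parameters will be performed at the local hospital laboratory". It adds that "The normal reference ranges and laboratory accreditation certificates must be provided to ETHICON", and that the laboratories do not know which treatment a child received. Eligibility in Protocol section 4.2 covers "Paediatric subjects aged ≥ 28 days (≥ 1 month) to <18 years". SAP section 8.2.1 plans "at least 40 randomized paediatrics subjects recruited from sites within the European Union and Canada".

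SAP section 10.2.2 lists Tables 14.3.2.1 (full blood count), 14.3.2.2 (white cell differential) and 14.3.2.3, the last titled "Laboratory data: Coagulation Parameters - Safety analysis set". Their notes give SI units and three time points. SAP section 10.2 sets the general layout: by treatment and, where suitable, by visit, with mean, SD, minimum, median and maximum. Age splits are named for effectiveness (Protocol section 8.3.2, SAP section 8.2) and, in the protocol only, for adverse events (section 8.4.2). None is named for laboratory data.

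The two documents differ on change from baseline. Protocol section 8.4.2 has laboratory results and their changes both listed and summarised, and then says "Clinically significant changes will be reported as part of the AE summary". SAP section 9.4 has them listed only, while SAP section 4 records no departure from the planned analysis.

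**The concern.** A platelet count or clotting time is judged against a range that can depend on the child's age and on the laboratory. The sponsor collects the ranges, yet no SAP text uses them to classify a result. Nor does it plan the other obvious remedy, a by-arm summary of each child's own change.

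Haemoglobin, haematocrit and platelets are named safety endpoints in SAP sections 3 and 9.1. Table 14.3.3, which gathers the safety endpoints, leaves them out, so the 14.3.2 tables are where they are summarised. As specified, a reader of those tables could not say how many children in each arm had a result that became abnormal after treatment. The laboratories are unaware of allocation, so a range-based count would be an objective safety measure in a trial that is otherwise open label.

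**Working it through.** The plan states no figure to reproduce, so the check is textual, followed by illustrative arithmetic. Document inputs: at least 40 children; allocation by "Treatment will be assigned randomly to each subject on a 1:1 basis to either EVARREST or SURGICEL treatment", so about 20 per arm; no age stratification described; and, for infants, "The next 4 subjects to be enrolled will be subjects aged ≥ 28 days to <1 year". All SDs and offsets below are assumptions.

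1. **Texts side by side.** Ranges are collected (Protocol 7.2.1), but the visible text of SAP 8.4, 9.1, 9.2, 9.4 and 10.2.2 contains no classification against them, no shift table and no out-of-range count. Protocol 8.4.2 summarises change and SAP 9.4 does not. The SAP 9.4 paragraph opens on adverse events and then mentions SI units, which do not apply to adverse events; it reads as though the laboratory subject was lost from the sentence. Taken literally it also leaves the values themselves unsummarised, against SAP 9.1.

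2. **One abnormal child and the arm mean.** A shift of k SD in 1 of 20 moves the mean by k/20. For k = 2, 3, 5 that is 0.10, 0.15, 0.25 SD. The standard error of the mean is 1/sqrt(20) = 0.22 SD.

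3. **Mixing ages and laboratories.** Let r be the between-age-and-laboratory SD divided by the within-group SD. The pooled SD grows by sqrt(1 + r^2): 1.12, 1.41, 1.80 for r = 0.5, 1.0, 1.5. A 3-SD outlier then looks like 3/1.12 = 2.7, 3/1.41 = 2.1 or 3/1.80 = 1.7 SD.

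4. **The same effect on a comparison of arm means.** The 95% half-width is 1.96 x sqrt(SDw^2 + SDa^2) x sqrt(2/20). With SDw = 10 and SDa = 0, 6, 10, 14 it is 6.2, 7.2, 8.8, 10.7 units. The units belong to no particular analyte, and the SAP plans no such interval.

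5. **Chance split of the 4 infants**, with 20 per arm and no stratification: P(x in one arm) = C(4,x) C(36,20-x) / C(40,20). A 2:2 split has probability 0.40, 3:1 either way 0.50, 4:0 either way 0.11. With an infant offset of d SD, a 4:0 split makes an arm difference of 4d/20: 0.2, 0.4, 0.6 SD for d = 1, 2, 3, with no treatment effect.

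6. **What change from baseline would do.** Write a result as a + w, where a is the child's stable age-and-laboratory offset. Post minus pre is w(post) - w(pre), so a cancels if it is additive and the same laboratory ran both tests. The pre-operative value's own variation remains, so this is a partial remedy.

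7. **Whether the visit columns can substitute.** Subtracting visit means gives the mean change only if the same children are in both columns, and never its spread. Protocol 7.1.1 requires only one pre-operative test, the one nearest surgery being used, so the screening and baseline columns may hold different children.

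**The case against.** The best defence is that nothing is concealed. SAP section 10.2 gives the minimum and maximum. Section 10.3 lists all non-administrative data by centre, child and visit, which is readable with about 40 children, and section 10.3.2 makes listings available for regular review. Clinically significant changes enter the adverse event summary under the protocol, and SAP section 8.4 tabulates clinically significant change since baseline. Bleeding and thrombotic adverse events, re-treatment, blood loss and transfusion are each summarised directly by arm, so laboratory data are supporting evidence. INR is by name a normalised ratio, which weakens the laboratory argument for it. Envelopes are issued to each site as a series, so allocation runs within site, although blocking is not stated.

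Much of this stands. A reader might infer that abnormal results are hidden, or that investigator judgement is the only route to them; the outputs just named rule out both. A reader might also infer that the ranges are never used. That cannot be asserted, because shell L sits in an attachment that was not supplied and could carry range flags. Nor do the documents say how many laboratories there are.

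What the defence does not supply is a count by arm. A minimum or maximum is one value from an age-mixed group and does not show whether it is abnormal for that child. Listings leave classification to the reader. The adverse event and clinically-significant-change items depend on judgement by staff who may know the allocation.

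**Conclusion.** The point holds as a gap in specification together with a conflict between the documents. The visible SAP text summarises blood counts and clotting tests only as SI values by arm and visit, pooled over age and local laboratory, and states no use for the ranges collected. It also drops the change summary that the protocol promises, which would have removed part of the age and laboratory offset. Abnormal results can be found, but they are not systematically tabulated by arm.

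The size cannot be fixed from the documents, which give no between-age or between-laboratory spread and no number of laboratories. The figures above rest on assumed offsets and about 20 per arm, and show direction only. It would be tempting to read the wider half-widths as lost precision in a planned comparison. They are not, because SAP section 9.4 plans no inference on safety data. No power, alpha, sample size or primary-endpoint result is affected. This is a worthwhile and inexpensive improvement to safety reporting.

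**What to change.** - Reconcile Protocol section 8.4.2 with SAP section 9.4 by restoring a by-arm summary of change from the last pre-operative value to the discharge value, and repair the SAP 9.4 sentence so that it names laboratory data.
- Add to Tables 14.3.2.1 to 14.3.2.3 a by-arm shift table (below, within, above range) between the same two time points for haemoglobin, haematocrit, platelets, white cells, PT, aPTT and INR. Use the performing laboratory's range for the child's age where available, and give the number newly out of range per arm.
- Flag out-of-range values in the laboratory listings, and keep the raw SI summaries.
- Optionally, summarise PT and aPTT divided by that laboratory's upper limit.
- Check shell L first. If it already carries range flags, the SAP text need only say so and define the classification.

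The cost is SAP wording, entry of reference ranges that the protocol already requires, and one shift table per panel. The downside is the work of matching ranges to age and laboratory. The protocol does not say that the ranges are age-specific, and some laboratories may supply only broad bands.
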